## 6.5. Exploratory Objective(s) (Cohort A)

### 6.5.1. To investigate the feasibility of using a daily activity diary to provide context in pediatric physical activity data collected by ActiGraph devices at home in pediatric participants.

MMRMs will be used to examine the association between Actigraph's activity metrics from the wrist sensor and the participants' responses from the daily activity diaries during the at-home monitoring period (Section 3.3, Table 6).

For each of the physical activity metrics, two models will be computed, one to investigate the effect of *Sickness or events preventing normal physical activity* and another to investigate the effect of *Sport* on that activity metric. In one model, *Sickness or events preventing normal physical activity* (yes/no) will be considered as categorical fixed effect and subject as the random effect. In the other model, *Sport* (no, yes > 30 mins, yes 30min - 1hr, yes > 1 hour) will be the categorical fixed effect, with subject as the random effect. Covariates such as age and gender may be utilized in both.

Autoregressive AR(1) variance-covariance structure will be used for the MMRM. The estimate of the coefficient for *Sickness or events preventing normal physical activity* / *Sport*, its standard error, 95% CI, and p-value will be derived. The model results will be presented in a table.

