- f. Varied speeds include participant's self-chosen slow pace ("Walk slow") and fast pace ("Walk fast").
- g. Participant will alternate between activities' stations. Participants will do ~7 minutes of activities, ~5 minutes of break and ~7 minutes of activities. The task stations include 2 sitting activities, 2 standing activities, and 2 walking activities. Order of stations will be determined at random using dice roll.
- h. Participants will complete activity diary (choice between either electronic or paper) at home daily between Day 2 and Day 15.
- i. The study staff will instruct the participants to mail back both ActiGraph devices at the final study evaluation over the phone at the exit interview.
- j. Any event with a device (issues with devices, loss of the devices, etc.), the impact of this event and the action taken with device will be recorded in a device assessment CRF.
- k. Adverse events (AEs) will be queried at the clinic visit and during the exit phone interview using open-ended and nonleading verbal questioning of the participant. Any spontaneously reported AEs noted during the home visits will be captured during the exit phone interview.

Abbreviations: → = ongoing/continuous event; APDM = Ambulatory Parkinson's Disease Monitoring.

COHORT B: PANORAMIC BRACELET SoA

Procedure/ Assessment	In-Lab		At-home monitoring															Final study evaluation	Return of Study Materials
	Screening	Visit 1	Day 1	Day 2	Day 3	Day 4	Day 5	Day 6	Visit 2	Day 8	Day 9	Day 10	Day 11	Day 12	Day 13	Day 14	Day 15		
	Day 1	Day 1							Day 7 +2									Day 15 (+3 days)	> Day 15
Informed Consent and Assent	X																		
Demography	X																		
Medical/Surgical History ^a	X																		
Prior/Concomitant treatment ^a	X																		
Inclusion/Exclusion criteria	X																		
Height, leg length ^b and weight		X																	
Edinburgh Handedness Inventory (EHI)-short form		X																	
Device exposure (APDM provisioning) ^c		X																	
Device exposure (In-Lab Panoramic Bracelet Device provisioning) ^d		X																	
Walking on GAITRite® walkway (~20 feet x 3) at participant's natural speed ^e		X																	

PFIZER CONFIDENTIAL

CT45-GSOP-RF15 2.0 Low-Interventional Study Protocol Template 05-Dec-2019

Page 29 of 76

Procedure/ Assessment	In-Lab		At-home monitoring															Final study evaluation	Return of Study Materials

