ANNEX 6. ACTIVITY DIARY

Instructions: Please answer these questions every day. If the child is 3 years old to 11 years old, the parent or legally acceptable representative should answer the questions. If the child is 12 years old or older, the child can answer the questions.

1) Were you sick today, or did anything prevent you from doing your normal physical activities (weather, other)?

Yes No

2) Today, did you do sports or physical activities in which you were very active (playing hard, running, jumping, throwing)?

Yes No

If Yes, what was the total time spent? <30 min 30 min - 1h > 1h

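### The planned Sport model (SAP 6.5.1) leaves out same-day sickness or prevented activity, so its sport contrasts are marginal and may absorb part of the sickness effect

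*SAP*

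**What the plan says.** SAP 6.5.1 covers the Cohort A exploratory objective on the daily activity diary. "For each of the physical activity metrics, two models will be computed, one to investigate the effect of" sickness or events preventing normal activity, and a second for sport. In the first model the sickness item ("yes/no) will be considered as categorical fixed effect and subject as the random effect") is the only diary term. In the second, sport ("no, yes > 30 mins, yes 30min - 1hr, yes > 1 hour) will be the categorical fixed effect") is the only diary term, again with a random subject effect. An AR(1) structure is specified. On adjustment the section says only: "Covariates such as age and gender may be utilized in both".

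Protocol Annex 6 puts both items on one form. Question 1 begins: "Were you sick today, or did anything prevent you from doing your normal physical activities (weather, other". Question 2 begins: "Today, did you do sports or physical activities in which you were very active (playing hard, running, jumping, throwing". The instruction is "Please answer these questions every day", and there is no skip from one question to the other.

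SAP 5.2 analyses observed data without imputation. No rule removes sick or prevented days from the Sport model. The protocol's Statistical Analysis section asks for the association between activity metrics and diary responses, and does not say whether the items should be modelled together or apart.

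**The concern.** Question 1 asks about being kept from normal physical activity, and question 2 asks about vigorous activity on the same day. A Yes to the first plausibly makes a Yes to the second less likely. With sickness absent from the Sport model, the no-sport level pools two kinds of day: ordinary days without sport, and days when the child was ill or prevented. If illness also changes sedentary time, light activity or counts apart from the lost sport, the sport contrasts carry some of that change.

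The other planned terms do not remove it. Age and gender are fixed or nearly so within a child over two weeks. The random subject effect absorbs differences between children, and AR(1) describes residual correlation. Sickness varies from day to day within a child.

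At stake is interpretation. The objective is to learn what context the diary gives to the activity data, and the SAP calls the coefficient an effect of sport. A reader would take it as what sport adds over an ordinary no-sport day, which is not quite what the model estimates.

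**Working it through.** **Inputs from the documents.** About 39 children in Cohort A. The diary schedule is "Participants will complete activity diary (choice between either electronic or paper) at home daily between Day 2 and Day 15", which is 15 − 2 + 1 = 14 days, so at most 39 × 14 = 546 child-days. There are two separate models with no sickness term in the Sport model. The documents give no sample size, effect size or variance for this analysis, so there is no planned figure to reproduce.

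**Assumed inputs (none is in the documents).** Share of sick or prevented days 5% to 20%; sport on 50% to 70% of other days and 0% to 30% of sick days; direct sickness effect g of −10, −20 or −40 min; day-to-day SD 20 min.

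**Formula.** Shift in a sport-versus-no-sport coefficient = −g × [P(sick | no sport) − P(sick | sport)].

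**Worked case.** 10% sick days, sport on 60% of other days and 10% of sick days:
- No sport: 0.10 × 0.90 = 0.09 sick and 0.90 × 0.40 = 0.36 other, so 0.09 / 0.45 = 0.200.
- Sport: 0.10 × 0.10 = 0.01 sick and 0.90 × 0.60 = 0.54 other, so 0.01 / 0.55 = 0.018.
- Difference 0.182. With g = −20 the shift is 20 × 0.182 = 3.6 min.

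**Range** (differences taken before rounding):

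| Sick days | Sport on other / sick days | P(sick, no sport) | P(sick, sport) | Difference | Shift, g = −20 |
|---|---|---|---|---|---|
| 5% | 60% / 30% | 0.084 | 0.026 | 0.059 | 1.2 min |
| 10% | 50% / 20% | 0.151 | 0.043 | 0.108 | 2.2 min |
| 10% | 50% / 5% | 0.174 | 0.011 | 0.163 | 3.3 min |
| 10% | 60% / 10% | 0.200 | 0.018 | 0.182 | 3.6 min |
| 20% | 60% / 10% | 0.360 | 0.040 | 0.320 | 6.4 min |
| 20% | 70% / 0% | 0.455 | 0.000 | 0.455 | 9.1 min |

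The shift halves at g = −10 and doubles at g = −40.

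**Simulation of the estimates.** 39 children × 14 days, random child intercept, AR(1) errors with correlation 0.3, three sport durations with true effects 10/20/30 min, g = −20, 100 replicates, fitted with a random intercept:
- 10% sick days, sport 60% / 10%: sport alone 14.0/24.0/33.4; with sickness added 10.4/20.3/29.8.
- 20% sick days, sport 60% / 10%: sport alone 16.7/26.5/36.8; with sickness added 10.2/20.1/30.3.
- Sport equally common on sick days: sport alone 9.8/19.6/29.9, so no shift.
- No direct sickness effect (g = 0): sport alone 10.4/20.0/29.8, so no shift.

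**Coverage of the sickness-adjusted contrast.** Take 10% sick days, sport 50% / 5%, g = −20. The no-sport level has 0.545 × 546 = 298 days. Each of three equal sport levels has 0.455 × 546 / 3 = 83 days. SE ≈ 20 × √(1/298 + 1/83) = 2.5 min, and the shift is 3.3 / 2.5 = 1.3 SE, so coverage ≈ Φ(1.96 − 1.3) − Φ(−1.96 − 1.3) ≈ 74%.

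Simulation with three levels, equal effects and a random intercept (200 replicates) gave 76%. With sport on 20% of sick days it gave 87%, and with g = −10 as well, 93%. With AR(1) errors and three levels, mild to moderate cases gave shifts of about +1 to +3 min and coverage of 79% to 94%. Coverage fell to 0% only in the extreme case of 20% sick days, no sport on them, sport on 50% of other days and g = −40: 0.20 / (0.20 + 0.40) = 0.333, and 40 × 0.333 = 13.3 min.

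**The case against.** The stated aim is exploratory and concerns feasibility and association. A one-item model validly estimates how activity differs between days answered Yes and No to sport. Against that target there is no bias, and coverage falls short only if the target is sport at fixed sickness. This stands: the planned model is not wrong, and the point concerns what its coefficient may be said to mean.

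A reader might infer that the two items are linked by design, so that a Yes to question 1 nearly always means No to question 2. The documents do not support that. Question 1 also covers weather and other causes, question 2 covers any very active play, and there is no skip between them. A negative association is plausible, but its strength is unknown.

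A reader might also infer that the sport interval fails badly. Collapsing sport to one yes/no coefficient gives 56% coverage at 10% sick days, sport 50% / 5% and g = −20. The SAP plans a four-level factor, so each contrast rests on fewer days, has a larger SE, and covers better at the same shift. All these figures rest on assumed inputs, and with 100 replicates even the correctly specified model ranged from 92% to 99%.

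The covariate sentence is an open list, so adding question 1 is permitted. It is not planned, however, and permission does not settle which contrast will be reported.

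Timing also counts. Cohort A's last visit was planned for 01 April 2022 and its interim report for 01 March 2023, while SAP version 3 is dated 01 September 2023. Replacing the pre-specified model now would, on those planned dates, be a change after data collection. This stands, and it limits the remedy to an addition.

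**Conclusion.** The point holds as a low-severity improvement. SAP 6.5.1 gives a marginal sport contrast whose no-sport reference includes sick or prevented days, and no planned term or exclusion separates them. Part of the sickness effect is credited to sport if two conditions both hold: sport is less common on such days, and sickness has its own effect on the metric. If either fails, the shift is zero.

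Under the assumed inputs the shift is about 1 min in mild cases, which is negligible, and about 3 min in moderate cases, with coverage of the adjusted contrast about 80%. Larger shifts need frequent sick days, almost no sport on them, or a large sickness effect. The true size cannot be derived from the documents. The Sickness model needs no change: without sport it reads as the total association of a sick or prevented day, which may act partly through less sport. No primary or secondary conclusion depends on this analysis.

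**What to change.** In SAP 6.5.1:
- Keep both planned models and label their coefficients as marginal associations.
- Add, for each metric, a Sport model with same-day question 1 (yes/no) as a fixed effect. Report its sport contrasts beside the planned ones, as the contribution of sport given sickness.
- As a check, refit the Sport model on days answered No to question 1.
- Tabulate question 1 against the sport levels by child-day, so the reader can see how far the items overlap.

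Label the added results supplementary, because Cohort A data collection was planned to end before SAP version 3. The cost is one more parameter in a model with up to 546 child-days. The variable is already on the same form, and no primary endpoint or analysis changes.

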Number of hours per day wearing the device and number of days with more than 10 hours of wearing for each participant will be recorded. Summary statistics will be provided for both endpoints for all participants and by age groups.

4. To evaluate the participant's or caregiver's perception of wearability and comfort of ActiGraph and APDM devices during in-lab sessions.

The wearability/comfort questionnaire for the in-lab session will be summarized by frequency and percentages. The study will further compare participant reported wearability and comfort from the exit questionnaire amongst locations (wrist and lumbar) using Wilcoxon signed rank test.

5. To evaluate the participant's or caregiver's perception of wearability and comfort of ActiGraph devices during the at-home monitoring period.

The wearability/comfort questionnaire during the at home period (Day 15+3 days) will be summarized by frequency and percentages. This study will compare responses from each of questionnaire amongst locations (wrist and lumbar) using Wilcoxon signed rank test.

6. To evaluate the effect of floor surface (carpet vs tile) on gait metrics collected using ActiGraph and APDM devices.

This study will quantify differences between sensor-derived gait quality metrics (from ActiGraph and APDM) collected on different floor surfaces using paired tests (t-test or Wilcoxon signed ranks test depending on normality of the data).

Tertiary/Exploratory objectives

1. To investigate the feasibility of using a daily activity diary to provide context in pediatric physical activity data collected by ActiGraph devices at home in pediatric participants. Mixed effects model with repeated measurement, ie, MMRM will be utilized to examine the association between ActiGraph measured activity metrics and participants' responses from the daily activity diaries across the whole at-home monitoring period.
2. To compare gait speed collected using the SIMI system and GAITRite® walkway, during in-lab sessions.

Accuracy of the measurements of gait speed will be determined by computing the mean absolute percent error between SIMI system and GAITRite® walkway and assess the bias using Bland-Altman plots and 95% limits of agreement. The agreement between SIMI system and GAITRite® walkway will be assed using ICC and its lower and upper limits.

COHORT B:

Primary Objectives

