### 3.5. Baseline Variables

Due to the nature of the study design, no baseline variables are defined.

Demographic variables (Section 3.4), floor type (carpet, tile), proximity of the device (Cohort B, Panoramic closer to wrist vs GENEActiv closer to wrist), and devices (GAITRite, APDM, Actigraph, GENEActiv, Panoramic Bracelet) may be adjusted as covariates in the statistical models.

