### Cohort A:

The comparisons between devices (e.g. APDM vs Actigraph) will be investigated with Mixed Model Repeated Measures (MMRM), ANOVA or a non-parametric equivalent (Kruskal-Wallis, Friedman tests). Necessary covariates will be included such as demographic variables such as age and gender, and floor type. Pairwise comparisons will be performed with paired t-tests or their non-parametric equivalent (Wilcoxon Signed-rank test). If visual inspection of the data suggests that a transformation of the endpoints should be performed, this will be applied as appropriate prior to analysis and documented in the final report as required.

P-values will be generated where appropriate and any p-value  $< 0.05$  will be considered statistically significant. If multiple p-values are generated, an experiment wise significance threshold will also be provided for context using methods such as family wise error rate (FWER) and/or false discovery rate (FDR) control. P-values will be rounded to 3 decimal places and therefore presented as 0.xxx; P-values smaller than 0.001 will be reported as '<0.001'.

Agreement between two measurements will be assessed by the intra-class correlation coefficient (ICC, type 2 way random effects, absolute agreement), according to the following benchmarks:  $ICC \leq 0.4$  indicates 'poor', 0.4 to 0.59 'moderate', 0.6 to 0.74 'good', and 0.75 to 1 'excellent' agreement. In addition, Bland–Altman plots and 95% limits of agreement (average difference  $\pm$  1.96 standard deviation of the difference) will be used to visualize and quantify differences between endpoints derived from the reference devices and comparator device (Actigraph).

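### The Cohort A diary models have no weekday/weekend term, so part of a shared weekend shift in activity can be credited to a diary answer whose frequency also differs at weekends

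*SAP*

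**What the plan says.** SAP 6.5.1 fits two models for each physical activity metric in SAP Table 6. In one, the sickness item (yes/no) "will be considered as categorical fixed effect and subject as the random effect". In the other, the four-level sport item "will be the categorical fixed effect, with subject as the random effect". For dependence between days, "Autoregressive AR(1) variance-covariance structure will be used for the MMRM". On adjustment the section says only: "Covariates such as age and gender may be utilized in both".

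The general rules add no day term. SAP 5.1 for Cohort A states: "Necessary covariates will be included such as demographic variables such as age and gender, and floor type". SAP 3.5 lists demographics, floor type, device proximity and device as variables that "may be adjusted as covariates in the statistical models". The protocol's Statistical Analysis section (Cohort A, tertiary/exploratory objective 1) describes the association with "participants' responses from the daily activity diaries across the whole at-home monitoring period" and names no calendar variable.

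The diary is completed daily from Day 2 to Day 15 (protocol, Cohort A Schedule of Activities, diary footnote).

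**The concern.** Written out, each model is: activity of child i on day t = intercept + diary answer(i,t) + child effect(i) + AR(1) error. Fourteen consecutive diary days always contain four weekend days, so every child with a full diary contributes both day types. A difference in mean activity between day types that is common to all children has no term of its own.

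The named elements cannot absorb it. AR(1) describes correlation between neighbouring days and does not model a shift in the mean on particular days. Age and gender are constant within a child over two weeks. If a diary answer is also given more or less often at weekends, its coefficient takes up part of the day-type difference.

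The objective asks whether the diary gives context to the device data, and the SAP describes the models as investigating the effect of sickness and of sport. The date already tells the analyst whether a day is a weekend day. Without a day-type term, the reader cannot tell how much of a diary coefficient repeats the calendar.

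**Working it through.** The documents give no sample size, effect size or power for this objective, so there is no figure of the plan to reproduce. The check asks how much of a weekend shift passes into the diary coefficient.

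**From the documents:** about 39 children in Cohort A (protocol, Study Size); diary on Days 2 to 15, so up to 14 days and 39 × 14 = 546 child-days; significance at p < 0.05 (SAP 5.1), taken as two-sided.

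**Assumed, not in the documents:** the weekend shift W, the answer rates on each day type, the between-child variance and the AR(1) correlation. The sport item is reduced to yes/no, and the true diary effect given the day is set to zero.

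**Formula.** Approximate bias without a weekend term = W × [P(weekend | yes) − P(weekend | no)], with weekend share 2/7.

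**Sport answered on 60% of weekdays and 35% of weekend days:**
- P(weekend | yes) = (2/7 × 0.35) / (2/7 × 0.35 + 5/7 × 0.60) = 0.1000 / 0.5286 = 0.189
- P(weekend | no) = (2/7 × 0.65) / (2/7 × 0.65 + 5/7 × 0.40) = 0.1857 / 0.4714 = 0.394
- Difference = −0.205, so about a fifth of the shift passes through
- W = −0.3 SD: bias = −0.3 × −0.205 = +0.06 SD
- W = −0.5 SD: bias = −0.5 × −0.205 = +0.10 SD

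Simulation of this case (39 children, 13 days, child ICC 0.4, AR(1) 0.2, 1,500 trials, generalised least squares with known covariance) gave the same biases, with false-positive rates of about 13% and 28%. With a weekend term the rate returned to about 5%.

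**Other settings** (39 children, 14 days, day-level SD 1, random-intercept variance 0.5, AR(1) 0.3, W = −0.5 SD, 1,500 trials each, no weekend term):

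| Yes-rate, weekday / weekend | Bias (SD) | False-positive rate |
|---|---|---|
| 50% / 50% | 0.00 | 5.4% |
| 50% / 40% | +0.04 | 9.4% |
| 50% / 30% | +0.08 | 16.9% |
| 50% / 70% | −0.08 | 16.9% |
| 5% / 10% (sickness-type) | −0.07 | 6.9% |
| 10% / 5% (sickness-type) | +0.06 | 7.1% |
| 10% / 2% (sickness-type) | +0.10 | 9.9% |

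In this set, adding a weekend term brought the mean diary coefficient to within 0.005 SD of zero and the false-positive rate to between 4.3% and 6.0% in every setting tried.

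The share passed through is 0% at equal rates, about 8% at 50/40 and about 16% at 50/30. It reaches 100% only if the answer coincides exactly with the weekend. For rare, sickness-type answers the bias is of similar size, but the coefficient is estimated less precisely, so fewer false positives result. The false-positive rates also depend on which SD the shift is scaled by. The bias formula does not.

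**The case against.** The strongest reply is that the plan asks about association, over "across the whole at-home monitoring period", as an exploratory feasibility question. The unadjusted association is a legitimate target, and what the diary adds beyond the calendar is a somewhat different question. This stands. It is why the adjusted estimate should sit beside the unadjusted one and not replace it.

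The covariate wording is also open-ended and would permit a weekend term. That is true, but it does not plan one, and the day-level variable that matters is not among the examples.

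The false-positive rates assume that sport has no relation to activity once the day is known. Protocol Annex 6 asks whether the child was very active, and the outcomes include vigorous and moderate-to-vigorous time, so a true null is unlikely for sport. This also stands: the bias is the more relevant measure.

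A reader might make four stronger inferences, and the documents support none of them:
- **That any change shared by all children on certain days is credited to the diary.** Only part is, and only if answer rates differ on those days.
- **That the sickness result is seriously compromised.** The false-positive inflation in the cases tried is small. Annex 6 also names weather, so some shared variation is what that item is meant to record.
- **That activity and answers drift over study days as novelty wears off.** Nothing in the documents sizes this, and it would matter only if the answers drifted too.
- **That every diary window contains school days.** The protocol's limitations section allows for holidays, Group 1 is aged 3 to 5, and school status is not collected. Only weekends are certain.

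**Conclusion.** The gap is real and its consequence is conditional. Neither SAP 6.5.1 nor the general covariate rules specify a weekday/weekend term, and nothing named in the models can stand in for one. If activity and answer frequency both differ by day type, the diary coefficient carries part of the weekend shift: about 0.06 to 0.10 SD for sport under the assumed 0.3 to 0.5 SD shift and 60% against 35% answer rates, and nothing if the rates are equal. The documents give neither the shift nor the rates, so the actual size in this cohort is unknown. The objective is exploratory and no primary or secondary result depends on it, so this is a worthwhile small improvement and does not invalidate the analysis.

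**What to change.** In SAP 6.5.1, add weekday/weekend, derived from the recorded date of the child-day, as a fixed effect to both the sickness and the sport model. Report these coefficients beside those from the unadjusted models, and say that the first describe association given day type and the second the overall association.

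The protocol's milestones planned the end of Cohort A data collection for 1 April 2022 and its interim report for 1 March 2023, and the current SAP is dated 1 September 2023. If the Cohort A models have already been run, label the adjusted ones a sensitivity analysis. A linear study-day term is optional. A school-day indicator should not be specified, because neither the diary in Annex 6 nor the participant data in SAP 3.4 records school status.

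The cost is SAP wording, one degree of freedom per model against at most 546 child-days, and one further set of estimates. Table 6 lists 11 metrics if each axis is counted, so 2 × 11 = 22 extra fits. The adjusted estimate also answers a slightly different question from the unadjusted one, which the report should state. No new data are needed.

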ANNEX 3. LIST OF PHYSICAL ACTIVITY METRICS ENDPOINTS

ActiGraph

- Sedentary time (min)
- Sedentary percentage (%)
- Light time (min)
- Light percentage (%)
- Life-style time (min)
- Life-style percentage (%)
- Moderate-to-Vigorous Physical Activity (MVPA) time (min)
- MVPA percentage (%)
- Total daily activity counts (on each axis, and vector magnitude of 3 axes)
- Total daily calories (calories)

Pfizer Wear Algorithm (GENEActiv, Panoramic Bracelet)

- Number of available hours (h)
- Number of hours of wear (h)
- Number of wear hours while awake (h)

Pfizer Sleep Algorithm (SleepPy - GENEActiv, Panoramic Bracelet)

- Time in Bed (min)
- Percent time asleep (%)
- Number of wake bouts (no.)

- Sleep onset latency (min)
- Wake after sleep onset (min)

[figure not shown]
Pfizer Scratch Algorithm (ScratchPy - GENEActiv, Panoramic Bracelet)

- Total scratch duration (min.)
- Total scratch episodes (no.)

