### 3.3. Exploratory Endpoints

**Table 6. Exploratory Objectives and Endpoints (Cohort A)**

 
• To investigate the feasibility of using a daily activity diary to provide context in pediatric physical activity data collected by ActiGraph devices at home in pediatric participants.
 
	
ActiGraph Physical Activity Endpoints from Wrist
 
 
• Light Activity Time (min)
 
• Moderate Activity Time (min)
 
• Vigorous Activity Time (min)
 
• Sedentary Activity Time (min)
 
• Non Sedentary Physical Activity (min)
 
• Moderate to Vigorous Physical Activity (MVPA, min)
 
• Calories (kcal)
 
• Total Activity Count for Axis X, Y, and Z
 
• Total Vector Magnitude
 
 
These parameters will be derived from the manufacturer's algorithms.
 
 
• Activity Diary 
 
1. Sickness or events preventing normal physical activity: Yes/No
 
2. Sport or very active physical activities: Yes/No
 
 
 

--	--

	
3. Length of time of sports or very active physical activities: <30 min, 30 min – 1 hr, > 1 hr

 
• To compare gait speed collected using the SIMI® system and GAITRite® walkway, during in-lab sessions.
 
	
 
• Gait speed measured by SIMI® system^28
 
• Gait speed measured by GAITRite® walkway derived during natural, slow and fast speed walk tasks
 

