#### 6.3.3. To assess the compliance in wearing the ActiGraph devices at home

Compliance information for at-home deployment will be based on wear time derived from both wrist and lumbar-worn ActiGraph device. First and last day will be removed for this analysis as we do not expect whole 24 hours of data.

For the wrist device, for each participant, the (a) *Wrist wear time*: Number of hours per day wearing the wrist device; (b) *Wrist compliant days*: Number of days with more than 18 hours of wrist wear time will be derived. Wear time will be obtained from the manufacturer's default parameter (Wear).

For the lumbar device, for each participant, the (a) *Lumbar wear time*: Number of hours per day wearing the lumbar device; (b) *Lumbar compliant days*: Number of days with more than 10 hours of lumbar wear time will be derived. Wear time will be obtained from the manufacturer's default parameter (Wear).

Summary statistics will be computed for these four endpoints across all participants and by age group. Box and whiskers plots of *wear time per day* (in hours and percentage of the day) across participants will be provided for both wrist and lumbar sensors.

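### The Cohort A diary models (SAP 6.5.1) analyse absolute daily wrist activity totals without accounting for that day's wear time, although SAP 6.3.3 already derives it

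*SAP*

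**What the plan says.** SAP 6.5.1 fits two mixed models to each Table 6 wrist metric, one for sickness (or another event that prevented normal activity) and one for sport. For the sickness model the wording is "yes/no) will be considered as categorical fixed effect and subject as the random effect". The sport model has the same form with a four-level factor. An AR(1) structure is specified. On covariates, 6.5.1 says "Covariates such as age and gender may be utilized in both".

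Every outcome in SAP Table 6 is an absolute daily amount. Typical entries are "Sedentary Activity Time (min", "Moderate to Vigorous Physical Activity (MVPA, min" and "Total Activity Count for Axis X, Y, and Z". Calories and total vector magnitude are also listed. Nothing is expressed per wear hour or as a percentage.

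Wear time is absent from the other places that could supply it:
- SAP 3.5 lists possible covariates as "Demographic variables (Section 3.4), floor type (carpet, tile), proximity of the device" and the device itself.
- SAP 4 defines one analysis set, all enrolled participants, with no minimum-wear rule for a valid day.
- SAP 5.2 uses observed data and plans no imputation.

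SAP 6.3.3 does handle wear, for the compliance endpoints only. It derives daily wrist wear hours, counts days above 18 hours, and states "First and last day will be removed for this analysis as we do not expect whole 24 hours of data".

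**The concern.** A daily total depends on how active the child was and on how long the watch recorded. The diary answers are plausible causes of a change in recording time: a watch may come off during sport or on a day in bed. The random subject effect takes up most of the stable differences between children. It does nothing about differences between one child's own days, and these drive the sickness and sport coefficients.

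Under SAP 5.2 a short-wear day enters the model at face value. The estimate, 95% CI and p-value would then be read as showing how well the diary explains activity, when part of the association could be wear. The protocol's section on limitations names poor wear compliance at home, so variable wear is expected.

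**Working it through.** The plan states no power, effect size or error rate for these models, so there is no figure to reproduce. The check has three parts.

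**1. Arithmetic for an outcome that accrues only while the watch is worn.** Recorded minutes = hourly rate × wear hours. Assume 2.5 MVPA minutes per wear hour (not in the documents):
- 24 h: 2.5 × 24 = 60 min
- 18 h, the wrist threshold in SAP 6.3.3: 2.5 × 18 = 45 min, which is 25% fewer
- 10 h: 2.5 × 10 = 25 min, which is 58% fewer

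The percentages follow from the hours alone (18/24 and 10/24) and do not depend on the assumed rate.

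**2. Direction for sedentary time.** Assume 15 h awake, 55% of it sedentary (neither figure is in the documents). Full awake wear gives 0.55 × 60 × 15 = 495 min.

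| Awake wear | Non-wear not scored | Non-wear scored as sedentary |
|---|---|---|
| 12 h | 0.55 × 60 × 12 = 396; difference -99 | 396 + 3 × 60 = 576; difference +81 |
| 8 h | 0.55 × 60 × 8 = 264; difference -231 | 264 + 7 × 60 = 684; difference +189 |

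The same loss of wear gives opposite signs under the two scoring rules. SAP Table 6 says only that the manufacturer's algorithms are used.

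**3. Simulation with no true sickness effect on hourly activity.**
- From the documents: about 39 Cohort A participants, and diary Days 2 to 15, so up to 14 days each (39 × 14 = 546 child-days).
- Assumed: 10% sick days; mean wear 21 h (SD 2 h, capped at 24 h); 2.5 MVPA min per wear hour; between-child SD 0.7 and day-to-day SD 0.6 min per hour.
- Model: random intercept, 200 runs per setting. The AR(1) structure was not simulated.

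| Wear deficit on sick days | Mean sickness effect, no wear term | p<0.05, no wear term | Mean effect, wear covariate | p<0.05, wear covariate |
|---|---|---|---|---|
| 0 h | -0.1 min | 6% | -0.2 min | 6% |
| 1 h | -2.1 min | 18% | +0.3 min | 4% |
| 2 h | -4.9 min | 70% | 0.0 min | 3% |
| 4 h | -10.0 min | 100% | -0.1 min | 3% |
| 6 h | -14.8 min | 100% | +0.1 min | 3% |

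The first row matters as much as the others: where wear does not differ by diary answer, there is no bias. Where it does, the spurious effect is close to the hourly rate times the deficit, and the covariate removes it under these assumptions.

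**The case against.** The strongest reply is that nothing forbids the adjustment. The covariate list in 6.5.1 is open-ended, and the Cohort A general methods in SAP 5.1 provide for covariates judged necessary. The wrist watch is to be worn continuously, which limits variation in wear. The objective is exploratory, concerns feasibility, and has no decision threshold. All of this stands. It makes the point one of pre-specification and of modest weight. It does not remove it, because no text commits to using a variable the SAP already derives.

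Four stronger readings are tempting, and the documents do not support them:
- **That the coefficients are biased, by 99 to 231 sedentary minutes for example.** No document gives wear by diary answer. That range needs 3 to 7 hours of lost awake wear on every affected day, and its sign reverses if non-wear is scored as sedentary.
- **That a partial Day 15 contaminates the models.** Cohort A wear continues to the final evaluation at Day 15 (+3 days), so Day 15 can be a full day. Day 1 has no diary entry and cannot enter at all.
- **That the SAP discarded ready-made wear-adjusted endpoints.** Protocol Annex 3 lists items such as "Sedentary percentage" but gives no denominator. If the denominator is the whole day, they do not correct for wear. The SAP version history also records a deliberate refinement of the activity metric list.
- **That the 18-hour rule should define the main analysis.** If wear falls on sick or sport days, the filter removes those days preferentially. It also misses some losses: with 15 h awake, a day with 12 h of awake wear plus 9 h overnight totals 21 h and passes.

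**Conclusion.** The point holds as a gap in specification. Both diary models in SAP 6.5.1 use outcomes that can depend on daily wear, and neither includes wear, although 6.3.3 derives it for the same device and period. The coefficients mix behaviour with wear only if wear differs within a child between diary answers. Whether it does cannot be judged from the documents, and for sedentary time even the direction is open.

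The simulated figures (about -2 to -15 MVPA minutes for deficits of 1 to 6 h) rest on assumed rates, variances and sick-day frequency. They show the mechanism and do not forecast this study's results. They also treat all wear hours as equally active, which waking and sleeping hours are not. Primary and secondary conclusions are unaffected, so this is a worthwhile minor improvement.

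**What to change.** In SAP 6.5.1:
- Add daily wrist wear hours, as derived in 6.3.3, as a covariate in both the sickness and the sport model. Alternatively, model minutes as a percentage of wear time and state that denominator. The percentage route suits only the minute endpoints, so counts and calories would still need the covariate.
- Tabulate daily wear hours by diary answer, so the reader can see whether the problem arose.
- State how the manufacturer's algorithm scores non-wear in each Table 6 metric.
- Exclude the actual day of device removal or return if it is partial, rather than Day 15 by default.
- Use the restriction to days above 18 h only as a sensitivity analysis, reporting how many sick and sport days it drops.

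The cost is one covariate, one table and a few lines of text. No new data are needed. Activity done while the watch was off still cannot be recovered. Cohort A's last visit was planned for 1 April 2022 and its interim report for 1 March 2023, both before SAP version 3 of 1 September 2023. If the diary results already exist, present the adjusted models as a labelled sensitivity analysis.
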